1.0 INTRODUCTION

This document outlines the statistical methods to be implemented during the analyses of data collected within the scope of Nektar Therapeutics Protocol 20-214-34 "A Multicenter, Phase 1b, Randomized, Double-Blind, Placebo-Controlled Trial of the Safety, Tolerability, Pharmacokinetics, and Pharmacodynamics of a Single Dose of Bempegaldesleukin (NKTR-214) Plus Standard of Care versus Placebo Plus Standard of Care in Adults with Mild COVID-19". The purpose of this plan is to provide specific guidelines from which the analysis will proceed. Any deviations from these guidelines will be documented in the clinical study report (CSR).

2.0 STUDY OBJECTIVES

2.1 Primary Objectives

- To evaluate the safety, tolerability, pharmacokinetics, and pharmacodynamics of bempegaldesleukin plus standard of care (referred to in this document as bempegaldesleukin/SOC) compared with placebo plus standard of care (referred to in this document as placebo/SOC) in patients with mild COVID-19 (coronavirus disease 2019; SARS-CoV-2).
- To evaluate the safety and tolerability of bempegaldesleukin administered as a single intravenous (IV) dose and to define the recommended Phase 2 dose (RP2D) of bempegaldesleukin in patients with mild COVID-19.
- To assess the effect of bempegaldesleukin on the time course and extent of changes in absolute lymphocyte counts.

2.2 Secondary Objectives

The secondary objectives listed below involve comparison of bempegaldesleukin/SOC versus placebo/SOC in patients with mild COVID-19:

- To estimate the incidence of adverse events (AEs).
- To evaluate the frequency of serious AEs (SAEs).
- To determine the percentage of patients who require supplemental oxygen.
- To evaluate clinical status based on the World Health Organization (WHO) Clinical Progression Scale.
- To assess the immunologic effects in blood before and after study drug administration, including effects on cytokines, natural killer cells, T-cells, and other serum proteins and immune modulators.

3.0 STUDY DESIGN AND PLAN

This is a multicenter, Phase 1b, randomized double-blind, placebo-controlled trial to assess the safety, tolerability, pharmacokinetics, and pharmacodynamics of bempegaldesleukin/SOC in adults with mild COVID-19, as well as to determine the RP2D of bempegaldesleukin. During the

study, patients will receive 1 dose of bempegaldesleukin or placebo and must remain in the hospital or be admitted to an in-patient facility for monitoring until at least Day 8.

Patients will be randomized (1:1 ratio) in groups of 10 patients (5 bempegaldesleukin/SOC and 5 placebo/SOC) in each cohort to receive one IV infusion of bempegaldesleukin in combination with standard of care or one IV infusion of placebo in combination with standard of care.

Eligible patients will be enrolled into 1 of 3 dose cohorts with doses ranging from 0.00075 mg/kg to 0.003 mg/kg. The first two patients randomized and treated in each dose cohort (1 with bempegaldesleukin/SOC and 1 with placebo/SOC) will serve as sentinel patients. Enrollment in each cohort will be staggered as follows. A Cohort Review Committee (CRC) will monitor blinded safety and tolerability data for the first 72 hours after study drug administration from the 2 sentinel patients before additional patients in that cohort are treated. If the CRC determines additional patients may be randomized, 2 patients will be randomized (1 with bempegaldesleukin/SOC and 1 with placebo/SOC), treated with study drug, and observed for 72 hours. For every 2 patients, the Medical Monitor will review the blinded safety and tolerability data for the first 72 hours after study drug administration to determine if the next 2 patients may be randomized. If it is not possible to assess the protocol defined DLT criteria (see Protocol Section 5.3.2.1.1), the Medical Monitor will request a review of the safety data by the CRC. After 10 patients have completed a 7-day observation period for dose-limiting toxicity (DLT; see Protocol Section 5.3.2.1 for additional details), the CRC will assess the accumulated, blinded safety and tolerability data, as well as any available pharmacokinetic, pharmacodynamic, and disease measurement data, to determine whether dose escalation or de-escalation from the tested bempegaldesleukin dose level is warranted. This decision will be based on blinded data using pre-defined criteria, including the proportion of patients who experience a DLT (see Protocol Section 5.3.1). Patients who drop out of the study for reasons other than a DLT, before the DLT evaluation period (Days 1 to 7) has elapsed, may be replaced.

The RP2D of bempegaldesleukin in patients with mild COVID-19 will be based on the totality of safety, tolerability, pharmacokinetic, pharmacodynamic, and disease measurement data.

4.0 DETERMINATION OF SAMPLE SIZE

This Phase 1b study will assess the safety and tolerability of different doses of bempegaldesleukin. No formal sample size calculation is done. Around 10 patients per dose cohort with a 1:1 randomization ratio (5 bempegaldesleukin/SOC and 5 placebo/SOC) to bempegaldesleukin/SOC or placebo/SOC will be enrolled. It is expected that a total of approximately 30 patients will be enrolled into the study.

5.0 GENERAL ANALYSIS CONSIDERATIONS

The statistical analyses will be reported using summary tables and data listings. Continuous variables will be summarized with means, standard deviations, medians, minimums, and maximums. Categorical variables will be summarized by counts and by percentage of patients in

corresponding categories. All summary tables will be presented by treatment. For patients who receive placebo, the data will be pooled as one placebo group.

Individual subject data obtained from the case report forms (CRFs) and any derived data will be presented by subject in data listings. Data listings will be sorted by the treatment group, subject, visit date, and time, if applicable.

All analyses and tabulations will be performed using SAS Version 9.4 or higher. All outputs will be presented in rich text format (RTF).

5.1 Definition of Common Variables

- Reference date (Day 1) = first dose date of study medication. If a patient has not been treated, the reference day will be set as missing.
- Study Day = assessment date reference date + 1 for assessments performed on or after the reference date or assessment date reference date for assessments performed before the reference date.
- Baseline: Baseline will be defined as the last non-missing value on or before the date of administration of the first dose of study medication (and time if available) unless it is identifiable by time that the value is after the first dose. For patients who have been not treated with any dose, then the baseline is defined as the screening value.

Time on study will be calculated as follows:

For visits/assessments/medications/therapies on or post study drug:

- Study hour will be calculated as follows:
- Study Hour = (assessment date time date time of the start of the first study dose)/60
- Study Day = (assessment date date of the first study dose) + 1, if assessment date is on or after the study dose date in that cohort
- Study Day = (assessment date date of the first study dose), if assessment date is prior to the study dose date in that cohort

For visit window derivation purpose, Study Day will be derived as ceiling of (Study Hour)/24.

For purposes of analysis and data display (i.e., means over time), actual visit hours/days are mapped to the planned study visit (i.e., nominal visits such as Hour 1, 2, Day 2, etc.) using visit windows. Acceptable visit windows around each scheduled procedure visit will be given for each measurement in the forthcoming sections. Due to the different data collection schedules for the various measurements, however, visit windows for different parameters might not be identical.

Unless otherwise specified, in mean and mean change from baseline/pre-dose summaries or analyses, if more than one value is obtained for the same measure within a given visit window,

the value closest to the planned study visit day and/or time will be used for reporting and analysis. If multiple values are equally away from the nominal visit day and/or time, the latter one will be used. However, for shift tables, the worst value mapped to that visit window will be used for summary purposes.

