1.2 Schedule of Events

Procedure / Period:	Screening	Т	reatment	Post-Treatment
Study Days ^a :	Days –7 to –1	Day 1	Days 2+ until Discharged ^a	Safety Follow-Up 30 days after discharge (± 7 days)
Informed consent	Х			
Inclusion/ exclusion criteria, including documentation of positive SARS-CoV-2 infection	х			
Medical history	Х			
Randomization		Predose		
Physical examination ^b	Х	Predose	Every day	
Vital signs, including SpO2 ^c	Х	Predose	Every day	
ECG ^d	Х			
Clinical data collection ^e		Predose	Every day	Call to patient ^r
Laboratory Assessments ^f		•		
Hematology and chemistry ^g	X (local lab)	Predose ^h (central lab)	Days 2, 3, 4, 6, 8 (central lab) ^j	
Coagulation ^g	X (local lab)	Predose ^h (central lab)		
Additional laboratory assessments	X (IL-6: local or central lab; other assessments: local lab)	Predose ^h (central lab)		
Serology HIV/HBV/HCV	X (local lab)			
Pregnancy test ^k	X (local lab)		Day 8 (local lab) ^j	
Urinalysis (dipstick)		Predose ^h (local lab)		
PK assessments ¹		Predose ^h and EOI ⁱ	Days 2, 3, 4, 6, 8 ^j	
Immunogenicity assessments ¹		Predose ^h	Day 8 ^j	Collect sample ^s

Schedule of assessments continued on next page.

Procedure / Period:	Screening	Treatment		Post-Treatment
Study Days ^a :	Days –7 to –1	Days 2+ until Day 1 Discharged ^a		Safety Follow-Up 30 days after discharge (± 7 days)
Biomarkers (central laborator	y only)	,	,	
Respiratory specimens for detection of SARS-CoV-2 nucleic acid ^{m,n}		Predose ^h	Days 4 and 8 ^j	Collect sample ^s
SARS-CoV-2 serology ^m		Predose ^h	Days 4 and 8 ^j	Collect sample ^s
HLA Haplotyping ^m		Predose ^h		
DNA/RNA sequencing ^m		Predose ^h	Days 4 and 8 ^j	Collect sample ^s
Immune cell profiling ^m		Predose ^h	Day 8 ^j	Collect sample ^s
Cytokine assessments ^m		Predose ^h	Days 2, 3, 4, 6, 8 ^j	
Study Drug Administration				
Study drug administration °		Х		
Hydration		X ^p	Days 2-4 ^p	
Standard of care ^q		As clinically indicated		
AE assessment	Х	Х	X ^t	Call to patient ^r
Review of concomitant medications	Х	Х	\mathbf{X}^{t}	Call to patient ^r

Table 1:Schedule of Events (Contd)

Abbreviations: AE = adverse events; ECG = electrocardiogram; EOI = end of infusion; HBV = hepatitis B virus; HCV = hepatitis C virus; HIV = human immunodeficiency virus; HLA = human leukocyte antigen;

PK = pharmacokinetics; SARS-CoV-2 = severe acute respiratory syndrome coronavirus 2; SpO₂ = oxygen saturation

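### SAP 5.1 gives no unit for the Study Hour difference: coded as written in SAS it yields minutes, so the visit-window Study Day is up to 60 times too large, and even with correct hours it disagrees with the date-based Study Day

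*SAP*

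**What the plan says.** SAP 5.1 contains two ways of obtaining a study day.

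- **Date-based.** Assessment date minus first-dose date, plus 1 for assessments on or after the dose date. The dose date is Day 1.
- **Hour-based, for visit windows.** The definition begins "Study Hour = (assessment date time" and ends "date time of the start of the first study dose)/60". The minus sign between the two date-times is missing from the extracted text, but the meaning is clear. The section continues: "For visit window derivation purpose, Study Day will be derived as ceiling of (Study Hour)/24".

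The purpose is given in the same section: "actual visit hours/days are mapped to the planned study visit (i.e., nominal visits such as Hour 1, 2, Day 2, etc.) using visit windows". The windows themselves are left to later sections.

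On software, SAP 5.0 says: "All analyses and tabulations will be performed using SAS Version 9.4 or higher". Protocol 1.2 schedules post-dose hematology and chemistry on "Days 2, 3, 4, 6, 8 (central lab"), with the dosing day as Day 1.

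**The concern.** Dividing by 24 makes sense only if Study Hour is in hours. Dividing a difference by 60 gives hours only if the difference is in minutes. SAP 5.1 does not say that it is, and in the named software a raw date-time difference is in seconds. A programmer who copies the formula would produce minutes under the label Study Hour.

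At stake is which record represents each nominal visit in summaries over time, and which value is chosen when a window holds several. SAP 5.1 relies on this mapping for means and mean changes from baseline. With about 5 bempegaldesleukin patients per cohort, a misplaced record would show in a summary.

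**Working it through.** **Inputs.** Divisor 60 and the rule ceiling(Study Hour/24), both from SAP 5.1. SAS 9.4 or higher, from SAP 5.0. Scheduled laboratory Days 2, 3, 4, 6 and 8, from Protocol 1.2. One assumption from outside the documents: a raw SAS date-time difference is in seconds. The range is therefore two cases, seconds or minutes.

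**Case 1: difference in minutes.** 24 h = 1440 min, and 1440/60 = 24. The divisor of 60 is then right and there is no unit error.

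**Case 2: difference in seconds, coded as written.** With h the true elapsed hours, Study Hour = 3600h/60 = 60h, and the window day = ceiling(60h/24). The last column applies the date-based rule; the rows at 20, 25 and 73 h assume a 09:00 dose for illustration, while at whole multiples of 24 h the result does not depend on the dose time.

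| True hours | Seconds | Seconds/60 | Window day as written | Ceiling with correct hours | Date-based day |
|---|---|---|---|---|---|
| 20 | 72,000 | 1,200 | 50 | 1 | 2 |
| 24 | 86,400 | 1,440 | 60 | 1 | 2 |
| 25 | 90,000 | 1,500 | 63 | 2 | 2 |
| 48 | 172,800 | 2,880 | 120 | 2 | 3 |
| 72 | 259,200 | 4,320 | 180 | 3 | 4 |
| 73 | 262,800 | 4,380 | 183 | 4 | 4 |
| 120 | 432,000 | 7,200 | 300 | 5 | 6 |
| 168 | 604,800 | 10,080 | 420 | 7 | 8 |

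**Size of the factor.** Study Hour is exactly 60 times too large. The window day is 60 times too large at whole multiples of 24 h and less elsewhere: 63/2 = 31.5 at 25 h and 183/4 = 45.75 at 73 h. From about 16 h onward the ratio lies between 30.5 and 60. Very early records escape: at 24 minutes, 1440 s/60 = 24 and ceiling(24/24) = Day 1.

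**Second discrepancy, independent of the unit.** Compare the last two columns. With correct hours, the ceiling gives Day 1 at 24 h and Day 7 at 168 h; the date-based rule gives Day 2 and Day 8, which matches the schedule. An alternative, floor(hours/24) + 1, gives 2 at 24 h and 8 at 168 h. It still misses a draw slightly short of a full day. After a 09:00 dose, an 08:00 draw the next morning is at 23 h: floor(23/24) + 1 = 1, while the date-based day is 2. This matters because Protocol 1.2 asks for morning hematology draws.

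**The case against.** The strongest reply is that SAP 5.1 is prose, not code. The result is called Study Hour and then divided by 24, so hours are plainly intended, and a competent programmer would convert. A Day 420 would stand out at once in a study whose latest follow-up contact is 38 + 7 = 45 days after Day 1. This stands in part. It makes a wrong reported result unlikely and keeps the point minor. It does not supply the missing unit, and it does not touch the one-day disagreement between the two day rules, which is less conspicuous.

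A reader might infer three stronger things that the documents do not support.

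- *Every post-dose record would miss its visit.* The window limits are not in the available text: SAP 5.1 defers them, and SAP 11.4 gives only the closest-value and tie rules. Records within about 24 minutes of dose start still give Day 1.
- *The lymphocyte time course, a primary objective, would be wrong.* The available SAP text runs from 7.6.4 to 9.0, so how lymphocyte counts are windowed cannot be seen. Protocol 9.7.1 asks for fold change at each evaluation time without saying how times are assigned. The link is possible, not shown.
- *All timing in the analysis is affected.* Date-based Study Day does not use Study Hour. The TEAE period (SAP 11.2) runs from the dose date. PK summaries and plots (SAP 9.0) use nominal and actual sampling times. Laboratory shift tables (SAP 11.5) take the worst post-dose grade.

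The line also lost its minus sign in extraction, so the divisor should be confirmed against the original file. Nothing suggests that the 60 itself was altered.

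**Conclusion.** The point holds as a minor specification error, conditional on coding the formula as written. Given seconds, Study Hour comes out in minutes and the visit-window Study Day is up to 60 times too large; given minutes, the formula is right and only the statement of the unit is missing. The documents do not settle which was meant. The reach is confined to records mapped to nominal visits through Study Hour.

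The disagreement between the hour-based and date-based Study Day does not depend on the software assumption. It is one day at every whole multiple of 24 h, so correcting the divisor alone would leave the section inconsistent.

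**What to change.** 1. Write Study Hour = (assessment date-time minus dose-start date-time, in seconds)/3600, or keep the 60 and state that the difference is in minutes.
2. In the same edit, reconcile the visit-window Study Day with the date-based one. The simplest choice is to use the date-based Study Day for day-level windows and keep Study Hour for hour-level visits. If an hour-based day is preferred, floor(hours/24) + 1 agrees with the schedule at whole days, but it must first be checked against the scheduled morning draws, because a draw just under 24 h after dosing would still fall to Day 1.

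The cost is a line or two of the SAP plus a programming check on the derived days. Data collection and trial conduct do not change.

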9.7.1 Pharmacodynamics

The fold change from baseline at each evaluation time and the maximum fold change of absolute lymphocyte counts will be summarized descriptively by treatment group and a data listing will be provided. Changes to these pharmacodynamic endpoints may be made in the SAP prior to database lock and unblinding of patient treatment assignment.

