11.3 Medical History

An event occurring after the patient has provided informed consent, but before the first dose of study treatment, will be collected as medical history unless the event is either new and attributed to protocol-mandated procedures by the Investigator or there is a significant change in the rate of occurrence or an increase in the severity of the pre-existing condition which is judged to be clinically important and attributed to the protocol-mandated procedures by the Investigator. Under the latter 2 circumstances, the event will be considered an AE and will be captured as such.

Medical history will be listed and summarized by System Organ Class and Preferred Term.

11.4 Visit Window for Safety Endpoints:

If more than one value is obtained for the same measure within a given visit window, the value closest to the planned study visit day/time will be used for reporting and analysis. If multiple values are the same number of days/times away from the nominal visit day/time, the latter one will be used.

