11.6 Vital Signs

Vital signs, including oxygen saturation (SpO₂), will be summarized using descriptive statistics at baseline and at each post-dose time point. Changes from baseline will also be summarized using descriptive statistics.

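### SAP 5.1 replaces the calendar Study Day with ceiling(Study Hour/24) for visit windows, which puts some samples one day early and lets scheduled Days 2/3 or 3/4 share one derived day

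*SAP*

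**What the plan says.** SAP 5.1 sets Day 1 as the date of the first dose. For assessments on or after that date it counts in calendar days: "Study Day = (assessment date date of the first study dose) + 1" (the minus sign between the two dates was lost in the PDF text). It also defines an elapsed time, "Study Hour = (assessment date time date time of the start of the first study dose)/60", and then uses it to redefine the day for one purpose: "For visit window derivation purpose, Study Day will be derived as ceiling of (Study Hour)/24".

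Actual times are to be mapped to planned visits through windows. The section promises that "Acceptable visit windows around each scheduled procedure visit will be given for each measurement in the forthcoming sections". When a window holds several values, the one closest to the planned visit is kept, and "If multiple values are equally away from the nominal visit day and/or time, the latter one will be used". SAP 11.4, the visit-window section for safety endpoints, opens with "If more than one value is obtained for the same measure within a given visit window" and repeats the closest-value and tie rules. It gives no window limits in the text available.

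Protocol Table 1 schedules post-dose hematology and chemistry on Days 2, 3, 4, 6 and 8, and vital signs every day. Its footnotes ask for hematology and chemistry to be drawn in the morning, and for predose samples within 3 hours before dosing. Nothing ties the clock time of later samples to that of dosing.

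**The concern.** The calendar rule and the ceiling rule are two different definitions of the same variable. They agree only when a sample is taken later by the clock than the dose was. Morning draws on later days can easily fall before the dosing clock time, because dosing follows the Day 1 predose work.

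A uniform one-day shift could be absorbed by suitable windows. A mixed pattern could not, because two scheduled days then carry one derived day and the distinction is lost before any window on that day is applied. A by-day summary could mix two scheduled days across patients, or drop one of a patient's two values.

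The outputs at risk are those summarised by windowed day. Vital signs "will be summarized using descriptive statistics at baseline and at each post-dose time point" (SAP 11.6). Hematology and chemistry are exposed if shown by visit. The protocol's pharmacodynamic summary includes "The fold change from baseline at each evaluation time and the maximum fold change of absolute lymphocyte counts" (Protocol 9.7.1), and the time course of lymphocyte counts is a primary objective. Protocol 2.1.3.1 expects a transient fall on Day 3 before the rise, so Days 2 to 4 are where a swapped value would distort the picture. With about 5 active patients per cohort, a few swaps can move a mean or median.

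**Working it through.** **Inputs.** Both day rules and the tie rule come from SAP 5.1; the scheduled days come from Protocol Table 1. The plan states no figure to reproduce. Clock times are not in the documents and are assumed below.

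**Step 1: general form.** For a sample on calendar Day D at clock time c, with dosing at clock time d, Study Hour is h = 24(D − 1) + (c − d). The ceiling rule gives ceiling(h/24) = D − 1 + ceiling((c − d)/24). As c and d differ by less than 24 hours, this equals D − 1 if c ≤ d and D if c > d. A comparison of the two rules in 15-minute steps, for dosing times from 06:00 to 19:45, found no exceptions.

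**Step 2: scheduled days.** Each cell shows h and the derived day.

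| Calendar Study Day | 15 min before dosing clock time | At dosing clock time | 15 min after |
|---|---|---|---|
| 2 | 23.75 h → 1 | 24 h → 1 | 24.25 h → 2 |
| 3 | 47.75 h → 2 | 48 h → 2 | 48.25 h → 3 |
| 4 | 71.75 h → 3 | 72 h → 3 | 72.25 h → 4 |
| 6 | 119.75 h → 5 | 120 h → 5 | 120.25 h → 6 |
| 8 | 167.75 h → 7 | 168 h → 7 | 168.25 h → 8 |

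**Step 3: shared days.** Two consecutive scheduled days share a derived day exactly when the earlier sample is after the dosing clock time and the later one is at or before it. Days 2/3 and 3/4 can therefore collide. Days 4/6 and 6/8 cannot: their possible labels are 3 or 4, 5 or 6, and 7 or 8. Windows that include the preceding derived day would restore Days 6 and 8, but not Days 2 to 4.

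Example: a Day 2 draw at 24.25 h and a Day 3 draw at 47.75 h are both derived Day 2. If distance is counted in derived days they tie. The later value is kept, so the Day 3 value is reported as Day 2 and the true Day 2 value is dropped.

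**Step 4: size under assumptions.** Take draws uniform over 06:00 to 12:00, independent between days, and a fixed dosing time. The share labelled one day early is p = (dosing hour − 6)/6. A patient has a shared day if Days 2/3 collide, with probability (1 − p)p, or Days 3/4 collide, with the same probability. These exclude each other, since the Day 3 draw must be at or before the dosing clock time in one and after it in the other. The total is 2p(1 − p).

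| Dosing time | p | 2p(1 − p) |
|---|---|---|
| 08:00 | 33% | 44% |
| 09:00 | 50% | 50% |
| 10:00 | 67% | 44% |
| 11:00 | 83% | 28% |
| 12:00 | 100% | 0% |

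Under a different assumption (dosing uniform over 09:00 to 13:00, draws uniform and independent over 07:00 to 11:00), a simulation gives about 87% of Day 2 draws labelled Day 1. About 8% of patients have a shared day for Days 2/3 and about 8% for Days 3/4.

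**Step 5: unit of Study Hour.** At 24 hours after dosing, a difference in minutes gives 1440/60 = 24 and Day 1. A difference in seconds gives 86400/60 = 1440, and 1440/24 = Day 60. The SAP does not state the unit.

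**The case against.** The strongest reply is that the derived day is only an intermediate variable. Values are mapped to nominal visits by windows, and windows could be set to absorb a uniform shift. In-patients drawn at a similar time each morning, before the hour at which they were dosed, would show just such a shift. That is correct, but it does not cover draws on both sides of the dosing clock time.

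The tie in the example also depends on how distance is counted. SAP 5.1 allows day and/or time. If nominal Day 2 is taken as 24 h, the two draws are 0.25 h and 23.75 h away and the true Day 2 value is kept. The Day 3 value still sits under derived Day 2. Windows using hours could separate the two, but the quoted sentence makes the derived day the basis.

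The percentages are assumption-driven, and the second set of assumptions gives much less collision. That stands.

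Confirmed exposure is narrow. PK concentrations are summarised by nominal time. Baseline and worst-grade shift tables are not shown to be affected. SAP 11.5 does not clearly summarise laboratory values by visit. Protocol 2.2.4.3 describes the lymphocyte endpoint of interest as the maximum between Days 6 and 8, which cannot collide with each other. The available SAP text runs from 7.6.4 to 9.0, so lymphocyte rules or window limits may lie in text that cannot be seen. All of this limits the impact. It does not remove the conflict in 5.1 or protect vital signs, whose section is visible. Listings sorted by visit date and time keep the true timing visible.

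**Conclusion.** The concern holds. As written, SAP 5.1 carries two Study Day rules, and the one chosen for windows is one day early for every post-dose sample taken at or before the dosing clock time. In mixed cases it merges scheduled Days 2/3 or 3/4, and daily vital signs can merge in the same way. This is certain as arithmetic. How often it happens is not known: 33% to 100% of samples shifted and 0% to 50% of patients with a shared day among Days 2 to 4 under the first set of assumptions, and about 8% per pair under the second.

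The analyses are descriptive and the error can be traced in the listings, so it does not threaten the trial. It should still be corrected before database lock. The missing window limits and the unstated unit are gaps in detail; the conclusion does not rest on them.

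**What to change.** In SAP 5.1, delete the ceiling sentence. Window day-level assessments on the calendar Study Day already defined there, or on the nominal visit. Under the calendar rule Days 2, 3, 4, 6 and 8 always keep their own labels and none is shared. Replacing the ceiling with floor(Study Hour/24) + 1 would not do: it changes only samples taken exactly at the dosing clock time.

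State the promised window limits on the same basis in SAP 11.4 and for lymphocyte counts, and state the unit of the date-time difference that is divided by 60. The cost is a few lines of SAP text and a small programming change before database lock, with no change to data collection.
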